## Protocol Summary

Title	Randomized, single-blind, placebo-controlled study on the effect of postoperative administration of single dose ketamine after mastectomy on pain
Short Title	Effect of postoperative single dose of ketamine on pain after mastectomy
Brief Summary	This is a randomized, single blinded, placebo-controlled trial to study the effectiveness of a subanesthetic dose (0.6mg/kg) of ketamine versus placebo (saline) on postoperative pain on adult women undergoing mastectomy.
Objectives	To examine the effect of a subanesthetic dose (0.6mg/kg) of ketamine vs. saline control on postoperative pain in subjects who have undergone mastectomy.
Methodology	Randomized, single blinded, placebo-controlled trial
Study Duration	Approximately 6 months
Participant Duration	7 days for 5 visits
Enrollment Period	Up to six weeks before surgery
Duration of Study Product Administration	At least 30 minutes at one time point
Population	Adults women, aged 18 to 80 years, who will undergo mastectomy
Number of participants	30 total participants (15 in treatment group, 15 in control group)
Description of Study Product (Ketamine) Administration	Ketamine[(+/-)-2-(2-chlorophenyl)-2-(methylamino)-cyclohexanone] is a white, crystalline powder or clear liquid. Ketamine at a dose of 0.6 mg/kg will be administered intravenously (IV) while the participant is recovering in the PACU. The study drug will be administered over at least 30 minutes at one time point and will be administered after subject has been deemed to be stable (hemodynamically stable, awake) by the study team on POD 0.
Reference Therapy	Saline. Saline is a prescription medicine used for fluid and electrolyte replenishment for intravenous administration. This is placebo drug in this study.
Key Procedures	IV administration of ketamine or saline Self-reported questionnaires Medical records review (opioid use and dosage assessments)
Statistical Analysis	Descriptive statistics will be used to summarize continuous variables. The normality of the distributions for continuous variables will be tested using Q-Q plots and Shapiro-Wilk tests. Differences between arms will be compared with two-sample t-test if outcome is normally distributed or with Wilcoxon's rank-sum test otherwise.

CONFIDENTIAL

This material is the property of the NYU School of Medicine and Langone Medical Center. Do not disclose or use except as authorized in writing by the study sponsor

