Thirty subjects undergoing mastectomy will be randomized to receive a single-bolus ketamine (0.6mg/kg) administered after surgery in the post-anesthesia care unit (PACU) or placebo (saline) control. All subjects will receive standard of care routine postoperative multimodal analgesia throughout hospital stay and after discharge. The Brief Pain Inventory (BPI) pain severity score at 24h and 48h post-surgery will serve as the primary endpoint. Secondary endpoints include responses on BPI (pain severity and interference subscales), opioid use, Quality of Recovery (QoR-15), National Institute of Health (NIH) Patient-Reported Outcomes Measurement Information System (PROMIS) scales for fatigue and sleep, Patient Health Questionnaire-2 (PHQ-2), Generalized Anxiety Disorder-2 (GAD-2), and Breast Cancer Pain Questionnaire. Side effects will also be assessed.

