### **3.2 Study Endpoints**

#### **3.2.1 Primary Study Endpoints**

Brief Pain Inventory-short form (BPI) pain severity subscale will be used as the primary endpoint at 24h and 48h postoperatively.

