## 10 Statistical Considerations

The primary outcome will be assessed with the BPI pain subscale at 24h postoperatively. We hypothesize subjects who received ketamine will have lower scores than those who received placebo. Secondary outcomes include changes in BPI (pain and interference subscales), PROMIS fatigue, PROMIS sleep, QoR-15, and BCPQ.

Descriptive statistics will be used to summarize continuous variables with mean and standard deviation, or categorical variables with frequency and percentage. The normality of the distributions for continuous variables will be tested using Q-Q plots and Shapiro-Wilk tests. If they are skewed, they will also be summarized using median and the inter-quartile range. A two-sided p-value<0.05 will be considered statistically significant. All analyses will be conducted using SAS 9.4 (SAS Institute Inc., Cary, NC).

CONFIDENTIAL

This material is the property of the NYU School of Medicine and Langone Medical Center. Do not disclose or use except as authorized in writing by the study sponsor

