### **10.1 Statistical and Analytical Plans (SAP)**

Descriptive statistics will be used to summarize the demographic and baseline characteristics, with mean and standard deviation for continuous variable, or frequency and percentage for categorical variables. If continuous variables are skewed, the median and inter-quartile range will be used as well. To test differences in the demographic and baseline characteristics between the two arms, clinical variables that are continuous will be compared using Wilcoxon's rank-sum test, and those categorical variables will be compared using the Fisher's exact test. The baseline balance will be determined by following both statistical and clinical significance criterion, with the latter as the primary.

The primary endpoints are the BPI pain subscale at 24 and 48 hours. The difference between ketamine and placebo will be compared using Wilcoxon's rank-sum test. A mixed-model repeated measures (MMRM) approach will be used to assess differences of repeated measures for the BPI pain subscales at 24h and 48h between two treatment regimes. The MMRM model will include the baseline pain subscale, factors for treatment, time, and treatment by time interaction. Unbalanced baseline variables will also be included. SAS PROC MIXED will be used to perform the analysis. Model-based least square means will be obtained for difference between two treatment arms at each time point.

Secondary endpoints include scales for postoperative pain, mood, fatigue/sleep, and recovery. The difference of secondary outcomes between ketamine and placebo will be compared using Wilcoxon's rank-sum test. In addition, for outcomes with single occasion (such as PHQ-2 and GAD-2 scales) linear regression models will be utilized to quantify the effects of the ketamine treatment against the control while controlling for their preoperative value and unbalanced baseline variables. Their model-adjusted pairwise differences will be quantified using point estimates associated with 95% confidence intervals. Outcome variables that are obtained on more than one occasion (such as BPI, opioid use and fatigue scales at 1+1, 2+2, and 7+2 days after surgery) will also be analyzed with an MMRM approach to assess differences between two treatment regimes. The MMRM model will include factors for treatment, time, treatment-by-time interaction, their preoperative values and unbalanced baseline variables.

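### The plan names 24 h in one place and 24 h plus 48 h in others as the primary endpoint, gives two methods for each time point, and never says which result decides

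*Combined protocol and SAP*

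**What the plan says.** **Time point.** Section 10 opens with one time point: "The primary outcome will be assessed with the BPI pain subscale at 24h postoperatively". Section 10.1 has two: "The primary endpoints are the BPI pain subscale at 24 and 48 hours". Section 3.2.1 also has two ("pain severity subscale will be used as the primary endpoint at 24h and 48h postoperatively"), as does section 1 ("pain severity score at 24h and 48h post-surgery will serve as the primary endpoint"). All of this is current text.

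**Method.** For the primary endpoints, section 10.1 first says "The difference between ketamine and placebo will be compared using Wilcoxon's rank-sum test". It then adds a mixed model for repeated measures (MMRM) with baseline pain, treatment, time and their interaction, and says "Model-based least square means will be obtained for difference between two treatment arms at each time point". On covariates it adds: "Unbalanced baseline variables will also be included". The Protocol Summary gives another rule: "Differences between arms will be compared with two-sample t-test if outcome is normally distributed or with Wilcoxon's rank-sum test otherwise".

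**Threshold and power.** Section 10 sets two-sided 0.05 for significance, with no split, order or adjustment. Section 9.1.1 gives 80% power for a standardised effect of 1.1 with 15 per arm, using a two-sided Wilcoxon test on normal data. It also describes the trial as a pilot without power for a hypothesised effect at 24 h and 48 h.

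**The concern.** A primary claim needs one identifiable result or a stated rule for combining several. Followed as written, the plan produces two primary tests at 0.05 if only the Wilcoxon test counts, and four results if the model contrasts count too. It does not say whether success at one time point is enough or both are needed.

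The two readings pull in opposite directions. If any one significant result is enough, the chance of a false claim exceeds 5%. If both time points must succeed, the false-positive rate is safe, but the stated 80% no longer describes the chance of success. Because the rule is unwritten, it can be settled after the results are seen. With 30 patients, a chance finding could then be presented as the primary result and carried into the design of a larger trial.

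**Working it through.** **Inputs from the documents.** 15 per arm, 1:1 allocation, two-sided 0.05, effect size 1.1, Wilcoxon test, normal data (sections 9.1.1, 9.2.1 and 10).

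**Assumptions, because the documents give no correlations.** Complete normal data; correlation between 24 h and 48 h of 0.3 to 0.8; correlation of baseline with each outcome of 0.2 to 0.4; for joint power, an effect of 1.1 at both times.

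**1. The plan's own figure.** For 15 against 15, the exact two-sided Wilcoxon test rejects when U ≤ 64 or U ≥ 161, with true size 0.0453. Simulated power at 1.1 is 79.5% (200,000 runs), so the stated 80% reproduces for **one test at one time point**. The two-sample t-test named in the Summary would have 82.8%, so the 80% belongs to the Wilcoxon test.

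**2. Simple bounds for two time points.**
- Two independent tests at exactly 0.05: 1 − (1 − 0.05)² = 9.75%.
- Two independent Wilcoxon tests at their true size: 1 − (1 − 0.0453)² = 8.9%.
- Both required, independent: 0.0453² = 0.2%.

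Positive correlation lowers the either-one figures and raises the both-required figure.

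**3. Simulation with correlated outcomes.** There were 40,000 runs for each of 12 correlation settings. The Wilcoxon test used exact p-values. The model contrast at each time point was a baseline-adjusted ANCOVA:

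estimate = (difference in outcome means) − β × (difference in baseline means),

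SE² = s² × [2/15 + (difference in baseline means)² / within-arm baseline sum of squares],

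referred to t with 27 df.

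| Rule for a positive primary result | False-positive rate |
|---|---|
| Wilcoxon, 24 h only | 4.5% |
| Either method, 24 h only | 6.2–7.0% |
| Wilcoxon, either time point | 7.3–9.0% |
| Adjusted contrast, either time point | 8.0–9.8% |
| Any of the four results | 9.8–13.2% |
| Wilcoxon, both time points | 0.4–1.8% |

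**4. Check of the ANCOVA stand-in.** A REML MMRM with unstructured covariance was fitted. At correlations 0.3 (between times) and 0.4 (baseline), 5,000 runs gave 9.5% for either contrast, 6.7% for either method at 24 h and 12.8% for any of four. At 0.8 and 0.2, 1,500 runs gave 9.9% for any of four. All agree with the ANCOVA results.

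**5. Power at effect size 1.1.**

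| Rule | Power |
|---|---|
| One Wilcoxon test at 0.05 | 79.5% |
| Wilcoxon at both time points, each at 0.05 | 65–72% |
| One Wilcoxon test at 0.025 | 70.4% exact; 68.6% normal approximation |
| One adjusted contrast at 0.05 | 81%, 83% and 87–88% for baseline correlation 0, 0.2 and 0.4 |

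At 0.025, about 80% power needs an effect of 1.22 (79.9%, exact) to 1.25 (80.9%, normal approximation).

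**6. Fixed sequence.** Test 24 h at 0.05, then 48 h at 0.05 only if 24 h is significant. If there is no effect at 24 h, a false claim first needs a false rejection there, which has probability at most 0.05. If there is an effect at 24 h, only 48 h can yield a false claim, again at most 0.05. The overall rate is therefore at most 5%, and the 24 h test keeps its 79.5% power.

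**The case against.** The best reply is that the plan points to the Wilcoxon test. It comes first in section 10.1 and is the only test behind the sample size. The MMRM's stated output is least-square means, and section 10.1 does not call its contrasts decision tests. On that reading the any-of-four rate rests on a rule that no section proposes. This has force: the better-supported figure is 7.3–9.0%, and 9.8–13.2% is a worst case. But no section says that the Wilcoxon test decides. Even on this reading, two time points remain at 0.05 each with no either/both rule, and section 10 still contradicts section 10.1.

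Second, this is a 30-patient pilot. Section 2 seeks only early evidence of efficacy, and section 5.1 says the study is not meant to support a new indication. That lowers the stakes, and strict error control matters less here than in a confirmatory trial. But section 10 states a directional hypothesis and a significance threshold, so the result that answers it should be identifiable.

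Third, section 9.1.1 does not claim 80% for joint success. That is right, and the figure is not an error. The text simply does not say which time point it covers.

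Fourth, the rates rest on assumed correlations and complete normal data, and the simulated model leaves out covariates added for imbalance. That stands. The effect of those covariates was not computed, nor was that of the t-test/Wilcoxon switch.

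Finally, a trial registration might fix the time frame. It would not make the protocol consistent and need not fix the test.

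**Conclusion.** The concern holds. The time-point conflict is plain in the text, and the missing decision rule changes what the trial can claim. The false-positive rate for the primary claim is 4.5% if one Wilcoxon test decides, 7.3–9.0% if either time point counts by Wilcoxon, and at worst 9.8–13.2% if any of four results counts. It is 0.4–1.8% if both time points must succeed, at the price of power near 65–72% instead of 80%. These ranges assume complete normal data, a 24 h/48 h correlation of 0.3–0.8 and a baseline correlation of 0.2–0.4. The conflict itself needs no assumption. Given the pilot setting, this should be fixed but does not undermine the trial.

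**What to change.** Before anyone sees unblinded outcome data, align the Protocol Summary and sections 1, 3.2.1, 10, 10.1 and 9.1.1 on one primary endpoint and one decision test. A workable version:

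- **Primary:** BPI severity at 24 h, two-sided Wilcoxon test at 0.05.
- **Next in sequence:** 48 h by the same test at 0.05, only if 24 h is significant.
- **Supportive:** the MMRM, with differences and 95% confidence intervals at each time point.
- **Protocol Summary:** delete the switch between t-test and Wilcoxon.
- **Section 9.1.1:** say that 80% power at 1.1 refers to one Wilcoxon comparison at 24 h.

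Alternatives, if the sponsor prefers them:

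- **MMRM contrast at 24 h as the decision test:** fix its covariates in advance (baseline BPI severity only, none chosen for observed imbalance) and restate power with the assumed baseline correlation.
- **Both time points primary, either may succeed:** split alpha and restate power as about 69–70% per time point at 1.1, or 80% at about 1.22–1.25.
- **Both time points required:** restate power as about 65–72%.

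The cost is wording, with no extra patients or data. Under the main proposal 48 h loses stand-alone primary status. Making the MMRM supportive gives up some power (79.5% against about 83–88%) if baseline pain correlates 0.2–0.4 with the outcome.

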#### **9.1.1 Sample Size Determination**

This is a pilot study with limited resources so that it is not powered to detect a hypothesized effect size for the BPI subscale at 24 hours and 48 hours. We expect to randomize 15 participants to each arm. With 15 subjects per arm, we have 80% power to test an effect size of 1.1 with a significance level (alpha) of 0.05 using a two-sided Wilcoxon's rank-sum test assuming data are generated from normal distributions.

### **9.2 Measures to Minimize Bias**

#### **9.2.1 Enrollment/Randomization/Masking Procedures**

The subjects will be randomized in a 1:1 ratio. The treatment subjects will receive 0.6 mg/kg of the study drug, and the control subjects will receive an equal volume of saline. Participants will be randomized with random size permuted blocks, blinded with respect to treatment assignments. [name] will generate the randomization list.

#### **9.2.2 Evaluation of Success of Blinding**

The subject will be asked if they know what group they were placed in at POD 1+1. If they are unsure that will be evaluated as successful blinding.

#### **9.2.3 Breaking the Study Blind/Participant Code**

In this single-blind study, the blind will not be broken.

### **11 Source Documents and Access to Source Data/Documents**

Source data is all information, original records of clinical findings, observations, or other activities in a clinical trial necessary for the reconstruction and evaluation of the trial. Source data are contained in source documents. Examples of these original documents, and data records include: hospital records, clinical and office charts, laboratory notes, memoranda, subjects' diaries or evaluation checklists, pharmacy dispensing records, recorded data from automated instruments, copies or transcriptions certified after verification as

CONFIDENTIAL

This material is the property of the NYU School of Medicine and Langone Medical Center. Do not disclose or use except as authorized in writing by the study sponsor

being accurate and complete, microfiches, photographic negatives, microfilm or magnetic media, x-rays, subject files, and records kept at the pharmacy, at the laboratories, and at medico-technical departments involved in the clinical trial. It is acceptable to use CRFs as source documents. If this is the case, it should be stated in this section what data will be collected on CRFs and what data will be collected from other sources.

The study case report form (CRF) is the primary data collection instrument for the study. All data requested on the CRF must be recorded. All missing data must be explained. If a space on the CRF is left blank because the procedure was not done or the question was not asked, write "N/D". If the item is not applicable to the individual case, write "N/A". All entries should be printed legibly in black ink. If any entry error has been made, to correct such an error, draw a single straight line through the incorrect entry and enter the correct data above it. All such changes must be initialed and dated. DO NOT ERASE OR WHITE OUT ERRORS. For clarification of illegible or uncertain entries, print the clarification above the item, then initial and date it.

Access to study records will be limited to IRB-approved members of the study team. The investigator will permit study-related monitoring, audits, and inspections by the IRB/EC, the sponsor, government regulatory bodies, and University compliance and quality assurance groups of all study related documents (e.g. source documents, regulatory documents, data collection instruments, study data etc.). The investigator will ensure the capability for inspections of applicable study-related facilities (e.g. pharmacy, diagnostic laboratory, etc.).

Participation as an investigator in this study implies acceptance of potential inspection by government regulatory authorities and applicable University compliance and quality assurance offices.

An electronic database capture system will be created to record the data for this trial. Research coordinators will input clinical trial data into the database. This database is password protected and only the PI, assigned study team members, and CTO staff will have access to the database. DataCore, a core resource of the institution, will provide the primary data collection instrument for the study. All data requested in the system must be reported. All missing data must be explained. The quality assurance specialists will monitor this trial every 3 months for data entry accuracy.

REDCap (Research Electronic Data Capture) is a secure web application capture system that will be created to record the data for this study. This database is password protected; the PI and designated study team personnel will have access to the database. REDCap is the primary data collection instrument for this study. All data requested in the system must be reported. All missing data must be explained. The quality assurance specialists will monitor this trial every 3 months for data entry accuracy.

Source documentation refers to original records of observations, clinical findings, and evaluations that are subsequently recorded as data. Source documentation should be consistent with data entered into any electronic medical record or REDCap. Relevant source documentation to be reviewed by the DSMC throughout the study includes:

1. Baseline measures to assess pre-protocol status
2. Concurrent medications
3. Treatment records
4. Adverse events

### **Data Collection**

Principal Investigator and IRB approved study personnel trained on this protocol will identify subjects. The following data elements will be captured from the subject's medical record and entered into the research database by the assigned data/research coordinator:

- age/ date of birth
- race

**CONFIDENTIAL**

This material is the property of the NYU School of Medicine and Langone Medical Center. Do not disclose or use except as authorized in writing by the study sponsor

- MRN
- gender
- ethnicity
- participant enrollment location
- zip code
- disease site

## 12 Quality Assurance and Quality Control

QC procedures will be implemented beginning with the data entry system and data QC checks that will be run on the database will be generated. Any missing data or data anomalies will be communicated to the site(s) for clarification/resolution.

Following written SOPs, the monitors will verify that the clinical trial is conducted and data are generated, documented (recorded), and reported in compliance with the protocol, GCP, and the applicable regulatory requirements (e.g., Good Laboratory Practices (GLP), Good Manufacturing Practices (GMP)).

The investigational site will provide direct access to all trial related sites, source data/documents, and reports for the purpose of monitoring and auditing by the sponsor, and inspection by local and regulatory authorities.

This study will be monitored according to the monitoring plan detailed below. The Investigator will also ensure that the monitor or other compliance or quality assurance reviewer is given access to all the above noted study-related documents and study related facilities (e.g. pharmacy, diagnostic laboratory, etc.), and has adequate space to conduct the monitoring visit. A risk-based, data-driven monitoring approach will be used to verify data for this trial which will also include a centralized review of data for quality, trends, consistency and general safety review. A quality assurance specialist will make regularly scheduled trips to the investigational site to review the progress of the trial, study data and site processes. At each visit, the monitor will review various aspects of the trial including, but not limited to: screening and enrollment logs; compliance with the protocol and study manual and with the principles of Good Clinical Practice; completion of case report forms; source data verification; study drug accountability and storage; facilities and staff.

During scheduled monitoring visits, the investigator and the investigational site staff must be available to meet with the quality assurance specialist in order to discuss the progress of the trial, make necessary corrections to case report form entries, respond to data clarification requests and respond to any other trial-related inquiries of the monitor. In addition to on-site monitoring visits, the Sponsor and/or representatives will also be routinely reviewing data. Any queries identified through this review will be managed within the systems established for query resolution and tracking. Inquiries related to study conduct, which require further information or action will be discussed within the study team for appropriate and documented escalation plans. It is expected that response to data clarification requests and other trial-related inquiries will occur throughout the course of the study through regular communication with the site monitor, the Sponsor or representatives, and review/entry of data into the electronic study database.

At any time during the course of the study, representatives of the FDA and/or local regulatory agencies may review the conduct or results of the study at the investigational site. The investigator must promptly inform NYULH PCC CTO and sponsor of any audit requests by health authorities, and will provide sponsor with the results of any such audits and with copies of any regulatory documents related to such audits.

In accordance with HIPAA and associated privacy regulations, a patient's authorization to use personal identifiable health information may be required from each patient before commencement of research activities. This authorization document must clearly specify what parties will have access to a patient's personal health information, for what purpose and for what duration.

CONFIDENTIAL

This material is the property of the NYU School of Medicine and Langone Medical Center. Do not disclose or use except as authorized in writing by the study sponsor

